**9. What is the postcode of your current home address?**

\_\_\_\_ (free text)

**10. This is an attention check. How many times have you visited the planet Mars?**

- Several times
- Just once
- Never

**11. Think of a ladder (see image) as representing where people stand in society. At the top of the ladder are the people who are best off—those who have the most money, most education and the best jobs. At the bottom are the people who are worst off—who have the least money, least education and the worst jobs or no job. The higher up you are on this ladder, the closer you are to people at the very top and the lower you are, the closer you are to the bottom. Where would you place yourself on the ladder?**

**Choose the number whose position best represents where you would be on this ladder:**

\_\_ (free text: range 1-10)

**12. On average, how much do you spend on supermarket shopping per week?**

£\_\_ \_\_

**13. How often, on average over the past year, have you shopped in a supermarket for food or groceries?**

- Less than once a month
- 1-3 times per month
- 1-2 times per week
- 3-4 times per week
- 5 times per week or more often

**14. How often, on average over the past year, have you shopped online for food or groceries?**

- Never or not in the last year
- 1-3 times in the last year
- 4-11 times in the last year
- 1-3 times per month
- once per week or more often

**15. Are you currently dieting?**

- Yes
- No

**16. Weight**

\_\_ . \_\_ kg

\_\_ st and \_\_ lb

**17. Height**

\_\_\_ cm

\_ ft and \_\_ in

## **APPENDIX F: ONLINE SHOPPING TASK INSTRUCTION**

*“We would like you to do online grocery shopping on a supermarket website. This is not a real commercial site, and you will not be asked to spend your own money.*

*You are given a shopping list and we ask you to buy all the items on the list. You can cross out the items on the list once you have added them to your trolley. You do not need to buy additional items. To search for the items from the shopping list, you can either go through the website categories or use the searching bar by copy-pasting the name of the shopping list item.*

*When doing the shopping task, please select foods you and your household would be likely to choose.”*

**APPENDIX G: HEALTH AND WEIGHT CONTROL MOTIVES**

**Instruction:** “Several different factors influence our choice of food. Read each item carefully and decide how important the item is to you. There are no right or wrong answers – we are interested in what is important to you”

**It is important to me that the food I eat on a typical day...**

		Not at all important 1	A little important 2	Moderately important 3	Very important 4
Health					
1.	contains a lot of vitamins and minerals				
2.	keeps me healthy				
3.	is nutritious				
4.	is high in protein				
5.	is good for my skin/teeth/hair/nails etc.				
6.	is high in fibre and roughage				
Weight control					
7.	is low in calories				
8.	helps me control my weight				
9.	is low in fat				

**APPENDIX H: DEBRIEFING QUESTIONNAIRE**

**Aim guessing:**

***What do you think we were expecting to find in this study?***

[Free text]

**Questionnaire:**

- ***What do you think this logo means?***  
*Select which of the following apply to the logo.*

- Lower in price option
- Fewer calories per gram option
- Lower in salt per gram option
- Lower in sugar per gram option
- Lower in saturated fat per gram option

- ***The choices I made during online shopping were influenced by how many calories I thought were in the options available.***

○	○	○	○	○	○	○
1	2	3	4	5	6	7
Strongly disagree	Disagree	Slightly disagree	Neither agree nor disagree	Slightly agree	Agree	Strongly agree

- ***I would normally buy [the 10 items on the shopping list]:***

	Never 1	Very Rarely 2	Rarely 3	Occasionally 4	Frequently 5	Very Frequently 6
Item 1						
Item 2						
Item 3						
Item 4						
Item 5						
Item 6						
Item 7						
Item 8						
Item 9						
Item 10						

- ***What is your highest educational qualification? If you are a student please select the diploma being studied for. \*Consistency check\****

- No formal qualifications

07/04/2020, pre-registered

- 1–3 GCSEs or equivalent
- 4+ GCSEs or equivalent
- A level or equivalent
- Certificate of higher education (CertHE) or equivalent
- Diploma of higher education (DipHE) or equivalent
- Bachelor or equivalent
- Master's degree or equivalent
- Doctorate or equivalent

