## Interventions

Participants will be randomly allocated to one of the following groups:

- default proportion & no labelling (D);
- default proportion & labelling (DL);
- increased proportion of lower ED food items & no labelling (I);
- increased proportion of lower-ED food items & labelling (IL).

The interventions will only be applied in the aisles and shelves of the online supermarket that include food items from the shopping list. Lower ED products will be defined in relation to a threshold for each aisle or shelf:  $\text{lower ED} \leq \text{median of ED distribution within a food category}$ .

In the *labelling* conditions (DL and IL) “healthier choice” badges will be added to the food item pictures when the above criterion is met. For *labelling* conditions only, instructions when logging-into the platform will introduce the badges to the participants: “In the online supermarket, the green tick allows you to see which products (e.g. muesli) in each product category (e.g. cereals) are healthier choices with fewer calories per gram than most other products in the same category.” The design of the badge is based on previous research investigating the effect of front-of-package nutrition labelling on food choices [23] (**Figure 1**).

**Figure 1.** Healthier choice badge display in the labelling conditions when  $\text{lower ED} \leq \text{median of ED distribution within a food category}$ .

In the *increased proportion* of lower ED food items conditions (I and IL) the proportion of lower ED vs. higher ED options will be reversed (67% lower ED – 33% higher ED) relative to the *default proportion* conditions (D and DL) (33% lower ED – 67% higher ED) (**Table 2**).

**Table 2.** Food items proportion and “healthy” labelling within a specific food category

	d1	d2	d3	d4	d5	d6	d7	d8	d9	d10
Default proportion No labelling	present	absent	absent	absent	present	absent	present	present	present	present
Default proportion Labelling	present healthy	absent	absent	absent	present healthy	absent	present	present	present	present
Increased proportion No labelling	present	present	present	present	absent	present	absent	absent	absent	present
Increased proportion Labelling	present healthy	present healthy	present healthy	present healthy	absent	present	absent	absent	absent	present

*di: food items in a given food category with ED ≤ ith decile of ED distribution within this food category*

Comments on Table 1:

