## 6. STUDY FLOW

RECRUITMENT (Prolific)	
 
▪ Predefined screening questions of Prolific website will be used to target the sample (Appendix A)
 
▪ Participants who will meet the inclusion/exclusion criteria will be e-mailed by Prolific and/or will be offered to complete our study on their Prolific account (Appendix B)
 
▪ Eligible participants who want to take part on the study will click on the start button and be redirected to our study website
 
			
INFORMED CONSENT (Qualtrics)	
 
▪ Participants will read the information sheet (Appendix C)
 
▪ Participants who want to proceed will tick a consent box (Appendix D)
 
▪ Participants will be allowed to contact the investigator via the “Contact researcher” button on Prolific webpage
 
			
BASELINE ASSESSMENTS (Qualtrics)	
 
▪ Participants will complete a baseline questionnaire on demographic, grocery shopping and health data (Appendix E)
 
			
RANDOMISATION (Qualtrics)	
 
▪ Participants will be randomly allocated to one of the four experimental conditions; same number of participants in each of the four groups.
 
			
	Default proportion & no labelling (D)	Default proportion & labelling (DL)	Increased proportion & no labelling (I)	Increased proportion & labelling (IL)
ONLINE SHOPPING TASK (Woods)	
 
▪ Instructions will be displayed (Appendix F)
 
▪ The shopping list will be displayed and participants will do the shopping task.
 
			
HEALTH AND WEIGHT CONTROL MOTIVES (Qualtrics)	
 
▪ Health and weight control food choice motives will be assessed – questions will be randomised (Appendix G)
 
			

DEBRIEFING (Qualtrics)	
 
▪ Aim guessing in an open-ended response format
 
▪ Insight on the participants' perception of the online shopping task (Appendix H)
 
▪ Text to tell the participants what the study was about (Appendix I)
 

---	--

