#### Debriefing questionnaire

We will explore whether the shopping list was valid and the extent to which participants reported being influenced by calorie content when making food choices. Responses to the debriefing questionnaire will be analysed.

- We will report the distribution of responses for *validity* and *kcal influence* (mean, SD, median, quartiles Q1 and Q3) in the overall sample.
- Two ANCOVAs will be run (as in primary analysis) to test the effect of *labelling*, *proportion* and *level of education* on (a) *validity* and (b) *kcal influence* to investigate whether the responses differ across conditions and SEP.

For the labelling conditions only, we will report the percentage of participants who know what the “healthier choice” badge means, i.e., who tick the answer “Fewer calories per gram option”.

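### The debriefing asks what the badge means just before it asks whether calories influenced choices, an avoidable priming risk for the labelling contrast on kcal influence

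*Combined protocol and SAP*

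**What the plan says.** Appendix H opens with the open-ended aim-guessing question. The questionnaire that follows lists, in this order:

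1. "What do you think this logo means", with five closed answers covering price, calories, salt, sugar and saturated fat. The calorie answer reads "Fewer calories per gram option".
2. The seven-point rating of "The choices I made during online shopping were influenced by how many calories I thought were in the options available".
3. The purchase-frequency ratings for the ten shopping-list items.
4. A repeat of the education question as a consistency check.

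Section 7.3 lists the second item (kcal influence) as a secondary outcome. Section 7.7, under the debriefing questionnaire, analyses it by ANCOVA on labelling, proportion and level of education "to investigate whether the responses differ across conditions and SEP". On the badge item, the same section says "For the labelling conditions only, we will report the percentage of participants who know what the" badge stands for.

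The study flow in Section 6 says of the motives questionnaire that "questions will be randomised". It says nothing of the kind about the debriefing.

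**The concern.** Kcal influence is the plan's only self-report of whether calories drove the choices made in the task. Its natural reading is the contrast between labelling and no labelling. The item printed immediately before it links the badge to calories as one possible meaning, and the badge is the intervention.

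If only participants who shopped with badges get that item, the cue coincides exactly with the factor being tested. A difference in kcal influence could then reflect the label in the shop, the reminder in the questionnaire, or both. No covariate or later analysis could separate them. The trial might then credit the labels with a greater use of calorie information that came partly from the order of two questions.

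**Working it through.** **Who sees the badge item.** The documents do not settle this. Section 7.7 limits the reporting of the item to the labelling arms. That fits showing it to those arms alone but does not say so. The two cases differ:

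- *Labelling arms only.* A shift of d SD caused by the preceding item enters the labelling contrast in full.
- *All four arms.* If the shift is d_L in the labelling arms and d_N in the others, the contrast is biased by d_L − d_N. Equal shifts cancel. Unequal shifts are possible, because only the labelling arms have met the badge.

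**Inputs.** Section 7.8 gives 788 participants, or 394 per labelling level. Section 7 sets p < 0.01 for secondary analyses.

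**The plan's own figure.** The documents give no sample size for kcal influence. The stated 788 is for a main effect of f = 0.1 on the primary outcome at 80% power and alpha 0.05. A noncentral F calculation (1 numerator df, 4 groups, 1 covariate, noncentrality f² × N) gives N = 787, or 788 in four equal groups, with power 0.8006 at 788. The figure reproduces.

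**Precision of the labelling contrast.** SE = √(2/394) = 2/√788 = 0.071 SD. The two-sided 0.01 threshold for an observed difference is 2.576 × 0.0712 = 0.18 SD. If the SD of the rating is 1.5 to 2.0 points (assumed), that is 0.28 to 0.37 scale points. This is a significance threshold and not an estimate of an order effect.

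**Chance of a false labelling effect.** With no true effect of labelling and a net order shift of d SD, the chance is Φ(d/SE − 2.576) + Φ(−d/SE − 2.576). The documents give no value for d, so the range is an assumption:

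| Net shift d (SD) | Chance of p < 0.01 |
|---|---|
| 0 | 1% |
| 0.05 | 3% |
| 0.10 | 12% |
| 0.15 | 32% |
| 0.20 | 59% |
| 0.30 | 95% |

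If all arms see the item and shift equally, the first row applies.

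**What cannot be affected.** Section 6 places the debriefing after the shopping task and after the motives questionnaire. Mean energy density, the other basket outcomes, the motive scores and the moderated mediation all use data collected earlier.

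**The case against.** A reader might infer that the labelling effect on kcal influence is contaminated as a matter of fact. The documents do not support that, for four reasons.

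- Bias needs a cue that acts differently by arm, and the plan does not say which arms are shown the badge item.
- The labelling arms were told before shopping that ticked products "are healthier choices with fewer calories per gram than most other products in the same category" (Section 5.1). The calorie meaning is already part of the intervention, so the debriefing item adds at most a reminder.
- Every arm has just rated the importance of food that "is low in calories" (Appendix G), so calories are not new to anyone at debriefing.
- The badge item gives no correct answer and offers four other meanings. It could draw some participants away from calories, so even the direction is open.

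It can also be said that kcal influence is absent from the objectives table in Section 2, that Section 7.7 treats it as exploratory, and that Appendix H gives no page layout or display logic.

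Most of this stands, and it limits the claim to a risk of unknown size and direction. It does not remove the risk. What participants learned before shopping belongs in the labelling effect, but a reminder afterwards does not. The motive item is common to all arms, refers to food on a typical day, and does not tie the badge to calories. The order in Appendix H is the only one documented.

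**Conclusion.** The point holds as an avoidable risk of priming on one exploratory, self-reported secondary outcome. The risk is clear if the badge item goes to the labelling arms only. If it goes to all arms, bias depends on the arms reacting differently.

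Its size cannot be derived from the documents. Over an assumed net shift of 0.05 to 0.20 SD, the chance of a false labelling effect at the 0.01 level runs from 3% to 59%. This assumes 394 analysed per labelling level and the printed order as the fielded order. A reader might take 0.18 SD as the expected bias, but it is only the difference that would reach significance at this sample size.

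The trial's primary conclusion is not at stake. The change is still worth making because it costs almost nothing before data collection and the problem cannot be repaired afterwards.

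**What to change.** State in Appendix H and Section 7.7 which arms are shown the badge item. Reorder the debriefing so that kcal influence precedes it: aim guessing, kcal influence, the ten purchase-frequency ratings, then the badge item on a later page with no way back.

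The cost is moving one question in Qualtrics. It adds no items, time or participants and does not change the sample size.

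There is a small downside. A calorie question placed earlier may slightly raise the percentage in the labelling arms who identify the badge's meaning. That figure is descriptive, and the ten ratings in between help to limit the carry-over.

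If the questionnaire has already been fielded as printed, the report should give the order and the routing of the badge item, and say that the labelling contrast on kcal influence may partly reflect question order.

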## **APPENDIX I: DEBRIEFING TEXT**

*“In this study we were interested in the effect of nutrition interventions on online grocery shopping. You have seen one version of the online supermarket but other participants have seen different ones. The difference between the four versions of the online supermarket is the food items they offer. In the first version, the food offer reflects what you can find in an online supermarket in the UK; in the second one low-energy badges are added to indicate the options with fewer calories per gram within a food category.; in the third one the proportion of lower-energy food items is increased; in the fourth one low-energy badges are added and the proportion of lower-energy food items is increased. We will compare the energy per 100g of the foods purchased by the participants from the four versions of the online supermarket. The results will help to identify the most promising intervention to reduce the overall energy of our diets.”*

*“Thank you very much for your participation in our study!”*
